1.1.3. Overall Design

This is a double-blind, randomized, placebo-controlled study of DCR-AUD to evaluate the safety, tolerability, PK, and PD of repeat doses of DCR-AUD in adult HVs.

Participants will receive 3 injections of study intervention (Day 1, Day 29, and Day 57), and have assessment visits through Week 24. Up to 10 EIAs will be conducted over the 24-week period to characterize the PD of DCR-AUD. For each EIA, participants will consume 4 standard drinks over the course of 80 minutes. Participants will be admitted to the clinic overnight for each EIA. At the discretion of the Investigator, participants who present with increasing positive ethanol reaction symptoms at the Day 169 EIA (flushing, headache, lightheadedness, palpitations, nausea, or vomiting) will be followed for an additional 4 weeks (through Day 197).

Table 1 presents the schedule of activities for the Screening, Dosing, End of Study, and Conditional Follow-up Visits. **Table 2** presents the schedule of activities for interim visits at which no study drug is administered. **Table 3** presents the schedule of activities for the EIA.

Number of Participants:

16 participants are planned for enrollment.

Intervention Groups and Duration:

Participants will be randomized 3 to 1 to DCR-AUD or placebo, administered at a dose of 480 mg once every 4 weeks at Days 1, 29, and 57.

Individual participants will be screened for a period of up to 4 weeks. Randomization and administration of the first dose of study intervention will occur on Day 1. Participants will return to the site for safety, tolerability, PK, and PD monitoring at specified time points as per the Schedule of Activities. Participants will be followed for approximately 24 weeks after the first injection of study intervention.

Study Population Key Criteria:

[figure not shown]
- Overtly healthy men and women aged 21 to 65 years.
- No diagnosis of AUD within the preceding 12 months per Diagnostic and Statistical Manual of Mental Disorders (DSM-5).
- Social drinkers who consume, on average, 5 to 20 drinks per week for men or 5 to 14 drinks per week for women over the 4 weeks prior to screening, and not more than 8 drinks in a single day.
- No evidence of overt or sub-clinical hepatic pathology, as manifest by serologic tests demonstrating hepatic inflammation or compromised hepatic synthetic function.
- No history of substance use disorder (SUD) or illicit drug use (excluding cannabis) within the preceding 12 months.

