- ^m Participants may be discharged from clinic following collection of the 24-hour postdose PK sample. Participants will return to clinic for collection of PK samples at 72 hours postdose on Days 4 and 32.
- ⁿ EIA will be conducted on the first day of the visit once all other assessments for that day have been completed. A total of 10 EIAs will be conducted. The timing of assessments and ethanol administration are detailed in [Table 3](#).
- ^o On dosing days, ECGs will be conducted approximately 30 minutes predose and 15-to-30 minutes postdose. If multiple assessments are due, the order of assessment should be ECG, vitals, PK, and then other assessments; with PK sample collection occurring at the nominal time. At Screening and EOS, one ECG will be performed. Screening ECGs may be repeated one time for determination of eligibility.
- ^p Blood pressure, if out of range at Screening, may be repeated one time for determination of eligibility.
- ^q Blood pressure and pulse rate to be recorded 15 (\pm 5) minutes postdose.
- ^r Height will be measured and recorded at Screening. Weight will be measured and recorded at every visit.
- ^s Sample to be collected prior to ethanol administration.
- ^t Hematology to include complete blood count with differential and RBC indices. See [Section 10.2](#) for a complete list of parameters.
- ^u See [Section 10.2](#) for a complete list of parameters.
- ^v Blood samples for complement testing to be collected predose and 2, 8, and 24 hours postdose on Day 1 and Day 57.
- ^w Blood sample for ADA testing to be drawn at same time as predose PK sample on Day 1.
- ^x Plasma samples for PK analysis to be collected predose and at 1, 2, 4, 6, 8, 24, and 72 hours postdose (exception: no 72-hour PK sample is required at Day 57). A single sample will be collected on Day 168. If multiple assessments are due, the order of testing should be ECG, vitals, PK, and then other assessments, with the PK sampling performed preferably at the nominal time point. A \pm 15-minute window will be allowed for collections at 1, 2, 4, 6, and 8 hours postdose. A \pm 30-minute window will be allowed for collection at 24 hours postdose. A \pm 60-minute window will be allowed for collection at 72 hours postdose.
- ^y Participants to record any symptoms associated with use of alcohol outside of in-clinic EIAs. Diary to be issued at time of discharge from clinic and collected and reviewed upon return to clinic.

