8.6.1. Ethanol Interaction Assessments

Serial EIAs will be performed to assess the indirect PD effects of ALDH2 reduction (acetaldehyde increase). EIAs will be conducted in accordance with the SoA in [Section 1.3](#). Should an EIA be missed, due to COVID-19 or other circumstances, the missed EIA may be conducted at an unscheduled visit at the discretion of the Investigator and the Sponsor.

Participants will be required to be fasted for at least 3 hours prior to administration of a standardized meal and must have a negative breath alcohol test on the day of the study visit prior to the EIA. Prior to each EIA, venous catheters will be placed at least 20 minutes before the first EIA vital signs are assessed at time 0. For EIAs conducted prior to a dosing day, the venous catheter will be left in place for PK sample collections.

Participants will consume a fixed dose of ethanol mixed in a liquid that has no additional alcohol, no caffeine, and is low in sugar. The ethanol dose will be 0.8 g/kg (to a maximum of 56 g) for male participants and 0.68 g/kg (to a maximum of 48 g) for female participants. Ethanol will be consumed in 4 equal aliquots over an 80-minute period (20 minutes for each

aliquot). During the EIA, participants will receive nothing by mouth (remain NPO) except water ad libitum. Assessments will be made over an estimated 4-hour period, as detailed in [Table 3](#).

Participants will remain in the Phase 1 unit for over-night observation. The Investigator will not discharge any participant experiencing ongoing effects of ethanol administration and will not do so until it is deemed medically safe to do so.

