9.4.2. Primary Endpoint(s)

The primary endpoints of the study are the assessment of the incidence and severity of AEs and SAEs, and the changes from baseline in vital signs, 12-lead ECG, clinical laboratory tests, and physical examination findings.

All safety analyses will be performed on the Safety Population. Adverse events will be defined as treatment-emergent AEs if they have a start date on or after the administration of study intervention during the treatment period. Frequency and percentages by treatment group will be used to summarize AEs, SAEs, AEs of special interest, and AEs by relationship.

Descriptive statistics and changes from baseline will be provided for vital signs, 12-lead ECG, clinical laboratory tests, and physical examination findings by treatment group and visit.

Laboratory parameter shifts from baseline to abnormal post-baseline values will be presented by treatment group. Mean laboratory values over time will be plotted by dose group.

By-participant listings will be provided for all the safety parameters.

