10.3.1. Definition of Adverse Event

An AE is any untoward medical occurrence in a patient or clinical study participant, temporally associated with the use of study intervention, whether or not considered related to the study intervention. An AE can therefore be any unfavorable and unintended sign (including an abnormal laboratory finding), symptom, or disease (new or exacerbated) temporally associated with the use of study intervention.

Events Meeting the AE Definition

- Any abnormal laboratory test results (hematology, clinical chemistry, or urinalysis) or other safety assessments (e.g., ECG, radiological scans, vital signs measurements), including those that worsen from baseline, considered clinically significant in the medical and scientific judgment of the Investigator.
- Exacerbation of a chronic or intermittent pre-existing condition, including either an increase in frequency and/or intensity of the condition.
- New condition detected or diagnosed after study intervention administration, even though it may have been present before the start of the study.
- Signs, symptoms, or the clinical sequelae of a suspected drug-drug interaction.
- Signs, symptoms, or the clinical sequelae of a suspected overdose of either study intervention or a concomitant medication. Overdose per se will not be reported as an AE/SAE unless it is an intentional overdose taken with possible suicidal/self-harming intent. Such overdoses should be reported regardless of sequelae.

Events NOT Meeting the AE Definition

- During the conduct of EIAs, participants will be questioned by site staff to assess the 6 symptoms (flushing, headache, lightheadedness, palpitations, nausea, and vomiting) associated with increased blood acetaldehyde levels. These symptoms solicited via active questioning do not meet the AE definition.
- Medical or surgical procedure (e.g., endoscopy, appendectomy): the condition that leads to the procedure is the AE.
- Situations in which an untoward medical occurrence did not occur (social and/or convenience admission to a hospital).
- Anticipated day-to-day fluctuations of pre-existing disease(s) or condition(s) present or detected at the start of the study that do not worsen.

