4.2.7 On-treatment assessment/event

The overall observation period will be divided into three mutually exclusive segments:

1. **screening period:** from day of participant's informed consent to before date of first administration of study treatment
2. **dosing period:** from date of first administration of study treatment to 58 days after date of last administration of study treatment (including start and stop date)
3. **follow-up period:** starting at day 58+1 after last administration of study treatment.

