4.13.1 Adverse Events

All outputs for AEs/treatment-emergent adverse events (TEAEs) will be based on the SP unless specified separately in TLF shells. Describe the AE dictionary including version that is to be used to classify the AEs.

All AE summaries should provide the number and percentages of participants reporting at least one AE and the total number of events reported.

Summaries of AEs will include the following:

- Incidence of AEs - Overview (by treatment and overall)
- Incidence of TEAEs (by treatment and overall, SOC, and PT)
- Incidence of TEAEs by maximum relationship (by treatment and overall, SOC, and PT)

- Incidence of TEAEs by maximum severity (mild/moderate/severe, by treatment and overall, SOC, and PT)

Summary tables will contain counts of participants, percentages of participants in parentheses, and the number of events where applicable. A participant who has multiple events in the same SOC and PT will be counted only once in the participant counts, but all events will be included.

All Adverse Events (AEs)

All AEs will be listed including pretreatment AEs.

Treatment-emergent Adverse Event

A TEAE will be defined as any AE that emerges during treatment (i.e., AE which started after study drug administration or pre-existed that worsened in severity after study drug administration) and those will be analyzed for the purpose of safety analysis.

TEAEs will be summarized by SOC and PT, including the number and percentage of participants experiencing events, separately.

Severity

TEAEs will be summarized by SOC, PT, and severity, including the number and percentage of participants experiencing events. If a participant reports the same TEAE more than once within that SOC and PT, the TEAE with the highest severity will be used in the corresponding severity summaries.

The summaries including severity will be reported by Common Terminology Criteria for Adverse Events (CTCAE) grade presented as below.

- Grade 1: Mild;
- Grade 2: Moderate;
- Grade 3: Severe or medically significant but not immediately life-threatening;
- Grade 4: Life-threatening consequences;
- Grade 5: Death related to AE.

participants who experience the same event multiple times will be included in the most severe category. Events with missing intensity will be considered as 'Grade 3' events for summary purposes but recorded as missing in the listings.

Relationship (Causality)

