6.2 Imputation Rules for Partial Dates

Imputed dates and time will NOT be presented in the listings.

Approved

Table 6-4 and Table 6-5 present algorithm for imputing partial dates for TEAE and prior/concomitant medication respectively.

Approved

Table 6-4 Algorithm for Treatment-Emergent Adverse Events:

Start/Increase Severity Date	Stop Date	Action
Known	Known	Considered as a treatment-emergent adverse event (TEAE) if start date on or after the date of the first dose of investigational product (IP)
	Partial	Considered as a TEAE if start date on or after the date of the first dose of IP. The last day of the month and the last month (ie, December) will be used if the stop day/month is missing.
	Missing	Considered as a TEAE if start date on or after the date of the first dose of IP
Partial, but known components show that it cannot be on or after first IP taken date	Known	Not a TEAE. The first day of the month and January will be used if the start day/month is missing.
	Partial	Not a TEAE. The first day of the month and January will be used if the start day/month is missing. The last day of the month and the last month (ie December) will be used if the stop day/month is missing.
	Missing	Not a TEAE. The first day of the month and January will be used if the start day/month is missing.
Partial, could be on or after first IP taken date	Known	Considered as TEAE, if stop date is after first IP taken date. The first IP taken date will be used if start date is in the same month/year with first IP taken date, or the first day of the month and January will be used if the start day/month is after first IP taken date Considered as not TEAE, if stop date is prior to first IP taken date. The first day of the month and January will be used if the start day/month is missing.
	Partial	Considered as TEAE. The first IP taken date will be used if start date is in the same month/year with first IP taken date, or the first day of the month and January will be used if the start day/month is after first IP taken date. The last day of the month and the last month (ie, December) will be used if the stop day/month is missing.
	Missing	Considered as TEAE. The first IP taken date will be used if start date is in the same month/year with first IP taken date, or the first day of the month and January will be used if the start day/month is after first IP taken date.
Missing	Known	Considered as TEAE if stop date is on or after the date of the first dose of IP.

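### SAP Table 6-4 assigns TEAEs by calendar date, so an AE that starts on Day 1 before the first injection is a TEAE there but pretreatment under SAP 4.13.1

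*SAP*

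**What the plan says.** The plan describes a TEAE in four places.

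- SAP 4.13.1, the definition: "AE which started after study drug administration or pre-existed that worsened in severity after study drug administration".
- SAP 6.2, Table 6-4, the row for known start and known stop dates: "Considered as a treatment-emergent adverse event (TEAE) if start date on or after the date of the first dose of investigational product (IP". The table sits under a heading on partial dates, but this row needs no imputation. Its first column covers the date of increased severity as well as the start date. It never refers to clock time.
- SAP 4.2.7 opens the dosing period by date: "from date of first administration of study treatment to 58 days after date of last administration of study treatment".
- Protocol 9.4.2: AEs are "defined as treatment-emergent AEs if they have a start date on or after the administration of study intervention". This compares a date with an act of dosing, so it does not settle an onset earlier on the same day.

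The schedule around the first dose is as follows. The first EIA is on Day -1, and "EIA will be conducted on the first day of the visit once all other assessments for that day have been completed" (Protocol 1.3, Table 1 footnotes). After an EIA, "Participants will remain in the Phase 1 unit for over-night observation" (Protocol 8.6.1). Then "Randomization and administration of the first dose of study intervention will occur on Day 1" (Protocol 1.1.3).

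On what counts as an AE, Protocol 10.3.1 exempts the six symptoms asked about during an EIA: "These symptoms solicited via active questioning do not meet the AE definition". Table 3 of the protocol counts events that participants volunteer, from the first sip of ethanol onward, as AEs. AEs are collected from consent (Protocol 8.3.1).

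**The concern.** A participant drinks up to 56 g (men) or 48 g (women) of ethanol on Day -1, sleeps in the unit, and on Day 1 volunteers a new headache or nausea before the injection. No study drug has been given. Under SAP 4.13.1 the event is pretreatment. Under Table 6-4 it is a TEAE. Neither document says which rule prevails.

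Many Phase 1 designs have nothing on the eve of dosing that would provoke such events, and the gap would be academic. Here the protocol schedules the provocation. Incidence and severity of AEs is the primary endpoint, reported as counts and percentages in arms of 12 and 4. Headache and nausea are also among the effects expected from acetaldehyde accumulation, so a pre-dose event in a TEAE table could be read as a drug effect.

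**Working it through.** **Rule check.** The documents give no clock times, so take a dose at 09:00 on Day 1 as an assumption.

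| Onset | Table 6-4 (date) | SAP 4.13.1 (after dosing) |
|---|---|---|
| Day -1, 21:00 | not a TEAE | not a TEAE |
| Day 1, 06:30 | TEAE | not a TEAE |
| Day 1, 10:00 | TEAE | TEAE |

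The rules disagree only in the middle row. An AE that began on Day -1 and merely persists keeps its Day -1 date and is classified correctly by both. An AE that worsens on Day 1 before the injection falls in the middle row.

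**Weight of one participant.** Arms are 12 and 4 (SAP 4.20). 1/12 = 8.3 points; 1/4 = 25 points.

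**When participant incidence changes.** SAP 4.13.1 counts a participant once per SOC and preferred term. Ten EIAs are planned (Protocol 1.3, Table 1 footnotes), one before the first dose and nine after it. Ethanol-related AEs volunteered after the later nine are TEAEs under either rule. A pre-dose event therefore adds a participant to a preferred-term row only if that participant does not have the same term again after dosing. The number of events changes in any case.

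**Chance of a change.** The documents give no rate. Let *p* be the chance that a participant has a pre-dose Day 1 AE of a given term after the Day -1 EIA. Assume the same chance of that term after each later EIA, independence across EIAs and participants, and all ten EIAs done.

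- Counted only because of the pre-dose event: *r* = *p*(1 − *p*)^9
- At least one such participant among *n*: 1 − (1 − *r*)^*n*

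| *p* | *r* | *n* = 16 | *n* = 4 (placebo) |
|---|---|---|---|
| 2% | 0.02 × 0.98^9 = 0.0167 | 24% | 7% |
| 5% | 0.05 × 0.95^9 = 0.0315 | 40% | 12% |
| 10% | 0.10 × 0.90^9 = 0.0387 | 47% | 15% |
| 20% | 0.20 × 0.80^9 = 0.0268 | 35% | 10% |

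The figures fall again at 20% because a common event is likely to recur after dosing. Positive within-person correlation would generally lower them. Missed EIAs would raise them.

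**Event counts.** The chance that at least one pre-dose event occurs at all is 1 − (1 − *p*)^*n*: 28%, 56%, 81% and 97% among 16, and 8%, 19%, 34% and 59% on placebo. These figures apply to the number of events, not to participant incidence.

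**The case against.** The best defence is that the two sections can be reconciled. Table 6-4 is introduced as a way to handle partial dates, so a programmer could apply 4.13.1 first and use the table only when a date is incomplete. Read literally, its date rule matches SAP 4.2.7 and is compatible with Protocol 9.4.2. Counting from the dosing date over-counts rather than misses events, which is a cautious convention for descriptive safety data. This shows that a date rule may be intended. It does not remove the conflict: the table is titled as the TEAE algorithm, it has a row for complete dates, and 4.13.1 says something else.

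There are safeguards. Investigators weigh timing when they assess causality (Protocol 10.3.4.3), so a pre-dose event should be called not related, and TEAEs are tabulated by relationship. All AEs, including pretreatment ones, are listed. Participants with a significant reaction on Day -1 leave before dosing (Protocol 7.1), so mainly milder events are at issue. These points stand, but the all-causality TEAE tables would still include the event.

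A reader might infer three stronger claims that the documents do not support:

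- That each pre-dose event moves incidence by 8.3 or 25 points. The once-per-term rule and nine later EIAs prevent that in many cases.
- That the comparison is biased towards one arm. The rule is the same in both arms and the events precede dosing.
- That the listings cannot resolve it. The SAP does not say whether they show onset time, and the table shells are separate documents.

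**Conclusion.** The inconsistency is in the text and is worth correcting, but its reach is narrow: volunteered AEs that start or worsen on Day 1 before the injection. If Table 6-4 is followed, ethanol effects that precede any study drug enter the primary-endpoint TEAE tables. This adds events, and sometimes participants, in both arms without a direction. The possible shift is 8.3 or 25 points per participant, conditional on no recurrence of the term. The probabilities above are illustrations that rest on assumed rates and independence, not predictions. With no formal testing of AEs planned, the cost is to the clarity of a small descriptive table.

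**What to change.** Use one rule in Table 6-4 and SAP 4.13.1:

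- If the start (or worsening) date equals the date of first dose and the time is known, the AE is a TEAE only if that time is at or after the time of first dose.
- If the time is missing, count it as a TEAE unless the record shows that it preceded the dose.

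The cost is a sentence in Table 6-4 and a cross-reference in 4.13.1. The SAP names a modification form for changes after finalisation. Dose date and time are already recorded (Protocol 6.4), and baseline already uses both (SAP 4.2.4). The four-hour rule for injection site reactions needs onset times for those events at least. The documents do not show whether the eCRF holds an onset time for every AE. If it does not, AEs dated Day 1 may need a query. No extra table or EIA flag is needed.

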Start/Increase Severity Date	Stop Date	Action
	Partial	The last day of the month and the last month (ie, December) will be used if the stop day/month is missing. If the imputed stop date is on or after the first dose of IP considered as a TEAE; if the year is missing, considered as a TEAE
	Missing	Considered as a TEAE

Approved

Table 6-5 Algorithm for Prior/Concomitant Medications Categorization:

Start Date	Stop Date	Action
Known	Known	If stop date is prior to the date for the first dose of IP, considered as prior; if stop date is on or after the date for the first dose of IP, considered as concomitant.
	Partial	The last day of the month and the last month (ie, December) will be used if the day/month of stop date is missing. If the imputed stop date is prior to the date for the first dose of IP, considered as prior; if the imputed stop date is on or after the date for the first dose of IP, considered as concomitant.
	Missing	Considered as concomitant.
Partial	Known	If stop date is prior to the date for the first dose of IP, considered as prior; If stop date is on or after the date for the first dose of IP, considered as concomitant. The first day of the month and January will be used if the start day/month is missing.
	Partial	The last day of the month and the last month (ie, December) will be used if the day/month of stop date is missing. If the imputed stop date is prior to the date for the first dose of IP, considered as prior; if the imputed stop date is on or after the date for the first dose of IP, considered as concomitant. The first day of the month and January will be used if the start day/month is missing.
	Missing	Considered as concomitant. The first day of the month and January will be used if the start day/month is missing.
Missing	Known	If stop date is prior to the date for the first dose of IP, considered as prior; if stop date is on or after the date for the first dose of IP, considered as concomitant.
	Partial	The last day of the month and the last month (ie, December) will be used if the day/month of stop date is missing. If the imputed stop date is prior to the date for the first dose of IP, considered as prior; if the imputed stop date is on or after the date for the first dose of IP, considered as concomitant.
	Missing	Considered as concomitant.

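### SAP Table 6-4: where a partial AE start could fall on or after first dose, a partial stop always gives TEAE, even with a stop month before dosing, and a known stop on the first-dose date has no class

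*SAP*

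**What the plan says.** Table 6-4 in SAP Section 6.2 first sorts AEs by what is known of the date of start or worsening, then by the stop date. Two of its blocks deal with partial starts.

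- **Start must precede dosing** ("Partial, but known components show that it cannot be on or after first IP taken date"). The class is the same whether the stop is known, partial or missing: "Not a TEAE. The first day of the month and January will be used if the start day/month is missing".
- **Start might not precede dosing** ("Partial, could be on or after first IP taken date"). With a known stop there are two conditions: "Considered as TEAE, if stop date is after first IP taken date", and "Considered as not TEAE, if stop date is prior to first IP taken date". With a partial stop the rule is unconditional: "Considered as TEAE. The first IP taken date will be used if start date is in the same month/year with first IP taken date". That row also completes the stop date to the last day of the month, or to December, but attaches no test to the result.

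Where the start is missing altogether, the stop date decides. For a known stop: "Considered as TEAE if stop date is on or after the date of the first dose of IP". For a partial stop: "If the imputed stop date is on or after the first dose of IP considered as a TEAE", and also TEAE if the stop year is unknown.

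The definitions that the table serves are in Protocol Section 9.4.2 (start on or after administration of study intervention) and SAP Section 4.13.1 (started, or worsened from a pre-existing state, after study drug).

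**The concern.** In the second partial-start block, two rows do not do their job.

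First, the partial-stop row can label as treatment-emergent an event whose recorded stop month shows that it was over before dosing. That contradicts both TEAE definitions. It also produces an odd ordering: with no start information the same stop date gives the right answer, and adding the start year turns it into the wrong one.

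Second, the known-stop row covers stops after and before the first-dose date but not on it. A programmer would have to supply a rule that the SAP does not contain.

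Incidence of AEs is a primary endpoint, and TEAEs are what the SAP tabulates. AEs are recorded from consent and screening lasts up to 28 days, so pre-dose events can be in the database. With 12 active and 4 placebo participants, a single wrong classification can be visible in a table.

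**Working it through.** The plan gives no figure to reproduce. The check is to write Table 6-4 as a decision rule and run date patterns through it.

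**Rule.** Let D be the first-dose date, S the latest date consistent with the recorded start, and E the stop date (imputed to month end or December if partial).

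- S < D: not a TEAE, whatever the stop.
- S ≥ D, start partial, stop partial: TEAE, with no test of E.
- S ≥ D, start partial, stop known: TEAE if E > D; not a TEAE if E < D; nothing stated if E = D.
- Start missing, stop known or partial: TEAE if E ≥ D (or the stop year is missing), otherwise by implication not a TEAE.

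**Example, assuming D = 15 Mar 2023.**

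| Recorded start | Recorded stop | E | Class under Table 6-4 |
|---|---|---|---|
| Feb 2023 | Feb 2023 | 28 Feb | Not a TEAE (S = 28 Feb < D) |
| 2022 | Feb 2023 | 28 Feb | Not a TEAE (S = 31 Dec 2022 < D) |
| Mar 2023 | Mar 2023 | 31 Mar | TEAE |
| 2023 | Mar 2023 | 31 Mar | TEAE |
| **2023** | **Feb 2023** | **28 Feb** | **TEAE, although E < D** |
| missing | Feb 2023 | 28 Feb | Not a TEAE |
| 2023 or Mar 2023 | 14 Mar 2023 | 14 Mar | Not a TEAE |
| **2023 or Mar 2023** | **15 Mar 2023** | **15 Mar** | **No class** |
| 2023 or Mar 2023 | 16 Mar 2023 | 16 Mar | TEAE |

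**Which partial/partial records go wrong.** If the start month is known and the stop month precedes the dosing month, the start cannot be later than the stop, so S < D and the first block classes the event correctly. A year-only start in an earlier year also has S < D. Only a year-only start in the dose year reaches the unconditional row with a stop month that is wholly before dosing.

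An enumeration confirms this. It takes all 365 dose dates in 2023, with start and stop in that year and the stop month wholly before dosing. For a dose date in month k there are k − 1 such stop months, and k(k − 1)/2 pairs of a known start month with a stop month.

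- Year-only start: sum over months of days × (k − 1) = 28×1 + 31×2 + 30×3 + 31×4 + 30×5 + 31×6 + 31×7 + 30×8 + 31×9 + 30×10 + 31×11 = 2,017. All are classed TEAE.
- Known start month: sum of days × k(k − 1)/2 = 28×1 + 31×3 + 30×6 + 31×10 + 30×15 + 31×21 + 31×28 + 30×36 + 31×45 + 30×55 + 31×66 = 8,751. All are classed not TEAE.

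These count date patterns. They do not estimate how many AEs will have them.

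**Size in a table.** SAP Section 4.2.6 uses N as the denominator. With the planned 12 active and 4 placebo, one participant is 1/4 = 25 percentage points on placebo and 1/12 = 8.3 on active. SAP Section 4.13.1 counts a participant once per system organ class and preferred term, so these are maxima: they apply only if the participant has no other TEAE in that cell.

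**The case against.** The strongest reply is that such records should hardly occur. Protocol Section 10.1.7 describes electronic capture in real time, with completeness checks and queries, and screening is at most 28 days, so a missing start month can usually be recovered. All AEs, including pretreatment ones, are listed, and imputed dates are kept out of the listings, so with 16 participants a reader could see the recorded dates. The SAP also resolves missing AE attributes cautiously (missing intensity becomes Grade 3, missing relationship becomes probably related), and defaulting to TEAE fits that habit.

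The point about frequency stands: the number affected may be zero. The point about caution stands only for events whose timing is unknown; it does not justify counting an event whose stop month shows that it ended before dosing. Nor does it give a class to a stop on the first-dose date.

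Nor can the first gap be closed by reading the stop month as moving the event into the block for starts that must precede dosing. Block membership depends on the start or worsening date, and the second block has its own branch for a known pre-dose stop.

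Three stronger readings are tempting and not supported:

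- *Every AE with two partial dates becomes a TEAE.* It does not: the first partial-start block classes such events correctly.
- *The Day −1 ethanol challenge will supply these events.* Reactions there arise in clinic under observation, and the six solicited symptoms are not AEs (Protocol Section 10.3.1). Day −1 falls in an earlier month than Day 1 only if Day 1 is the first of a month.
- *The imputed start will fall after the imputed stop.* The first-dose date is imputed only when the start shares its month and year with first dose; a year-only start does not clearly meet that condition.

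**Conclusion.** Both gaps are real but narrow, and this is a correction of the lowest severity. Both lie in the block for partial starts that could fall on or after first dose. The first misclassifies an AE only when the start is recorded as the dose year alone and the stop month is known and before dosing. The second affects a partial-start AE in that block with a known stop on the first-dose date.

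The documents give no frequency for such records, so no expected effect can be stated. The figures of 25 and 8.3 percentage points are ceilings for one participant in one cell. They assume that the planned 12 and 4 participants are dosed and that the participant has no other TEAE in that cell.

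**What to change.** In Table 6-4, within the block for partial starts that could fall on or after first dose:

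1. **Partial-stop row.** Impute the stop (last day of the month; December if the month is missing). Class as TEAE if the imputed stop is on or after the first-dose date or the stop year is missing; otherwise not a TEAE.
2. **Known-stop row.** Change *after* to *on or after* in the TEAE condition.

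Both rows then match the missing-start rows. In the worked example, start 2023 with stop Feb 2023 becomes not a TEAE, a stop on 15 Mar 2023 becomes a TEAE, and no other pattern tested changes class.

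The cost is two lines of SAP wording and the matching program logic, with no change to data or conduct. SAP Section 1 already provides a Statistical Method Modification Form for changes after finalization.
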